### 3.11 Operational definition

#### A. Control Group with Bone Wax:

Group of patients who undergo cardiac surgery with the use of cardiopulmonary bypass and use Bone Wax to protect the sternum after median sternotomy.

#### B. Treatment Group with Sternum Guard™:

Group of patients who undergo cardiac surgery with the use of cardiopulmonary bypass and use Sternum Guard™ to protect the sternum after median sternotomy.

Table 1 - Table of Operational Definition

	Variable	Definition	Type of Data	Code
1	Age	The age of participant when undergo the cardiac surgery, it defines with calculated birth year taken from the medical record	Numerik	
2	Gender	Gender which is included in this study are based one the	Categorical	1 = Male 2 = Female

		data recorded in the medical record.		
3	Comorbid	Data extracted from anamnesis and the medical record, with blood pressure $\geq 140/90$ mmHg and diabetes mellitus (Fasting Blood Glucose $>126$ mg/dL or 2 hr post prandial blood glucose or one time blood glucose $>200$ mg/dL)	Categorical	1 = Yes 2 = No
6	Cardiac Surgery	Any cardiac surgery that are conducted in adult cardiac surgery division which are using cardiopulmonary bypass	Categorical	1 = CABG 2 = Valve 3 = CABG + Valve 4 = Vascular
7	Surgical Site Infection	Surgical site infection is divided by 2 categories (Superficial: infection occurs just in the area where the incision is made; Deep: occurs beneath the incision area in muscle and the tissues surrounding the muscle). It is evaluated at day 0, at the end of hospital stay, day 14 post – operative and day 30 post-operative	Categorical	1 = Deep 2 = Superficial
8	Sternal Dehiscence	Occurs when there is an evidence of sternum separation. Often	Categorical	1 = Yes 2 = No

[figure not shown]
		accompanies with mediastinitis.		
9	Haemostasis Effect	The data obtained by quantity of blood lost from the sternal edges in Sternum Guard TM and Bone Wax group. The Sternum Guard TM and sterile drapes will be weighed digitally before and after surgery to estimate the blood lost.	Numeric	
10	Satisfaction Rate	The result obtained by the questionnaire in both groups.  Overall satisfaction rate  Maintenance of a dry surgical field during intervention (both groups)  Haemostatic effect  Ease of insertion (Sternum Guard TM group)  Ease of removal (Sternum Guard TM group)	Categorical	1 = Satisfied 2 = fairly satisfied 3 = fairly dissatisfied 4 = dissatisfied
12	Experience satisfaction rate	The result obtained by the questionnaire for the Sternum Guard TM group.	Categorical	1 = worse 2 = similar 3 = better

13	Uncontrolled Diabetes Mellitus	A fasting plasma glucose (FPG) level of 126 mg/dL or higher, or a random plasma glucose of 200 mg/dL or higher, or hemoglobin A1c (HbA1c) level of 6.5% or higher.	Categorical	1 = yes 2 = no
14	Uncontrolled Hypertension	An average Systolic Blood Pressure of $\geq 140$ mmHg or an average Diastolic Blood Pressure of $\geq 90$ mmHg, among those with hypertension	Categorical	1 = yes 2 = no

### 3. 12 Ethics

This study will be reviewed by the committee ethics in the National Cardiovascular Centre Harapan Kita.

### 3. 13 Research flow

### 3.14 Dummy table

#### Participant Characteristic

Table 2 - Dummy Table 1

	Sternum Guard™		Bone Wax	
	N	%	N	%
Age **				
Male *				
CABG *				
CABG + VALVE*				
VALVE *				
VASCULAR *				
Hypertension *				
Diabetes Mellitus *				
CPB time < 60 minutes *				
CPB time > 60 minutes *				

\*) n(%)

\*\* ) mean + SD

#### Outcomes

Table 3 - Dummy Table 2

	Sternum Guard™		Bone Wax	
	N	%	N	%
Primary Outcomes				
Surgical Site Infection:				
Superficial *				
Deep *				
Sternal Dehiscence:				
Yes *				
No *				
Haemostasis Effect (gr)**				
Satisfaction Rates **				
Satisfied				
Fairly satisfied				
Fairly dissatisfied				
Dissatisfied				

\*) n(%)

\*\* ) mean + SD

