## **1.3 Research Questions**

Is Sternum Guard™ more effective than Bone Wax application intraoperatively in reducing surgical site infection and sternal dehiscence for post cardiac surgery patients?

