## **1.4 Hypothesis**

We hypothesize that Sternum Guard™ is more effective than Bone Wax in reducing surgical site infection and sternal dehiscence for post cardiac surgery patients.

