**Specific Objectives:**

1. To compare the surgical site infection and sternal dehiscence rates at the end of hospital stay, day 14 post operation, and day 30 post operation in post cardiac surgery patient with the application of Sternum Guard™ as opposed to bone wax intraoperatively.
2. To compare the haemostasis effect of Sternum Guard™ as opposed to bone wax intraoperatively in cardiac surgery.
3. To compare the satisfaction rate (includes global satisfaction rate, haemostasis and dryness of surgical site, and mechanical protection) of the surgeons who are using the Sternum Guard™ as opposed to bone wax intraoperatively in cardiac surgery.

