### **3.8 Variable identification**

Independent variable in this study included the patient that are eligible for cardiac surgery. Dependent variable in this study are the assessment of surgical site infection and sternal dehiscence, haemostasis effect in Sternum Guard™ and Bone Wax group, and satisfaction rates of the surgeons.

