### **3.9 Data analysis**

All collected data will be verified and will be statistically analyzed using SPSS and the result from the data analysis was considered statistically significant with a p-value of  $< 0.05$ . For descriptive analysis, we will perform the analysis independently for numerical and categorical data. All numerical data will be analyzed using Coefficient of Variance and confirmed by Kolmogorov-Smirnov normality test. Normally distributed data will be analyzed using mean and standard deviation, meanwhile the abnormally distributed data will be analyzed using median, minimum value and maximum value. Categorical data analysis will be presented by percentage and frequencies table.

For inferential data analysis, we will perform the comparison tests and mean comparison test. The proportion comparison tests are applied for comparing categorical independence variable between Sternum Guard™ and bone wax group, such as Chi-square test and Fisher's Exact test as an alternative for chi-squared test. Mean comparison tests are utilized for comparing numerical independence variable between Sternum Guard™ and bone wax group, such as Independent T-Test and Mann-Whitney test for the non-parametric test.

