### **3.10 Clinical outcome indicators and assessments**

1. Surgical site infection: assessment of the surgical site infection includes the types of infection (deep and superficial), sternal dehiscence, and percentage of the surgical site infection and sternal dehiscence. The participants will be assessed at day 0, at the end of the hospital stay, day 14 post - operative, and day 30 – post operative. All of the sternotomy wound will be documented digitally at day 0, at the end of the hospital stay, day 14 post – operative, and day 30 post-operative.

2. Haemostasis effect: It will assess the quantity of blood lost from the sternal edges in Sternum Guard™ and Bone Wax group. The Sternum Guard™ and sterile drapes will be weighed before and after surgery to estimate the blood lost.
  
3. Satisfaction Rate: The satisfaction rate will be evaluated using a questionnaire distributed to the surgeons. The questionnaire will contain overall satisfaction, ease of placement, maintenance of a dry field throughout the surgery, ease of removal; each of this question will have four different response which are satisfied, fairly satisfied, fairly dissatisfied, dissatisfied. Additionally, the surgeons will be asked about the experience in using Sternum Guard™ as compared to Bone Wax and it will contain 3 different response: worse, similar, better.

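### The plan names no single primary outcome, main visit or success rule: it does not say whether SSI, sternal dehiscence or both must improve, and those rules give different answers

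*Combined protocol and SAP*

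**What the plan says.** - **Table 3 (3.14)** is the only place that ranks outcomes. Its single outcome heading, "Primary Outcomes", stands above superficial SSI, deep SSI, sternal dehiscence, haemostasis effect and satisfaction rates. There is no secondary heading and no visit column.
- **1.3 and 1.4** ask and hypothesise whether the device is "more effective than Bone Wax in reducing surgical site infection and sternal dehiscence for post cardiac surgery patients". Neither says whether a benefit on one outcome is enough.
- **1.5, objective 1** compares "surgical site infection and sternal dehiscence rates at the end of hospital stay, day 14 post operation, and day 30 post operation". No visit is the main one.
- **3.8** lists the outcomes side by side: "Dependent variable in this study are the assessment of surgical site infection and sternal dehiscence, haemostasis effect", then satisfaction.
- **3.10, item 1** files dehiscence inside SSI: "assessment of the surgical site infection includes the types of infection (deep and superficial), sternal dehiscence". **Table 1 (3.11)** makes it a separate variable with its own definition, "Occurs when there is an evidence of sternum separation", and Table 3 also lists it separately.
- **3.7** sizes the trial on 0.15 versus 0.05 without naming the outcome or visit.
- **3.9** states that "the result from the data analysis was considered statistically significant with a p-value of" below 0.05. It gives no order of testing, composite or adjustment.

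**The concern.** A confirmatory trial needs one pre-set answer to the question of what result counts as success. Here at least three rules fit the text: SSI or dehiscence improves, both improve, or a combined event improves. They differ in false-positive risk and in power. If the two outcomes disagree, nothing in the plan says which rule applies, so it could be picked with the results in view. Table 3 also gives satisfaction the same standing as the clinical outcomes, although it is scored by surgeons who know the allocation (3.5).

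**Working it through.** **Inputs**
- From 3.7: two-sided 5%, power 90%, proportions 0.15 and 0.05, total 376, inflated to 414.
- Allocation: two groups (3.5). Table 6 budgets 207 devices, and 414/2 = 207, so 1:1 is taken.
- Quoted rates: SSI 1.3-12.8% (1.1) and dehiscence 0.5-8.4% (2.7). These are literature ranges; using them as day-30 rates is an assumption.
- Assumed middle case: SSI 5%, dehiscence 2%.
- Overlap is not given. Assumed: dehiscence independent of SSI, or 50% or 90% of dehiscence cases in SSI patients. Full overlap was also checked at the top rates.
- Test: 3.9 names chi-square with Fisher's exact test as the alternative but no switching rule. Assumed: Fisher when an expected count is below 5. Fisher throughout is shown as a sensitivity case.

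**Step 1: the plan's own figure.** Mean proportion = (0.15 + 0.05)/2 = 0.10.

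n = [1.960 × √(2 × 0.10 × 0.90) + 1.282 × √(0.15 × 0.85 + 0.05 × 0.95)]² / 0.10² = 187.05, so 188 per arm and 376 in total. The stated figure reproduces, for one unnamed proportion at 5%.

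**Step 2: simple bounds with no true effect, two independent 5% tests.**
- Either suffices: 1 − 0.95² = 9.75%.
- Both required: 0.05² = 0.25%.
- Either, counting only errors favouring Sternum Guard: 1 − 0.975² = 4.9%, against a benchmark of 2.5%.

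Overlap pulls these together. At the top rates, with every dehiscence in an SSI patient, simulation gives 7.9% for either and 2.2% for both.

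**Step 3: simulated two-sided false-positive risk** (188 per arm, day 30 only, at least 40,000 trials per setting; ranges span the overlap assumptions).

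| SSI / dehiscence | Either suffices, chi-square with Fisher if sparse | Either suffices, Fisher throughout |
|---|---|---|
| 12.8% / 8.4% | about 8-10% | about 5.6-6.6% |
| 5% / 2% (assumed) | 6-7% | about 4.1-4.5% |
| 1.3% / 0.5% | about 1% | about 1% |

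If both are required, the risk is about 2% or less. One composite tested once at the top rates gives 4.8-5.2%. Expected events per arm explain the gradient: 188 × 0.084 = 15.8 dehiscences at the top rate, but 188 × 0.02 = 3.8 in the middle case, where Fisher's test is conservative.

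**Step 4: results when the device works.** Take a threefold reduction in both outcomes, the ratio in 3.7 (0.15/0.05 = 3).

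| SSI / dehiscence (control) | Exactly one significant | Both significant | Composite significant | SSI significant |
|---|---|---|---|---|
| 12.8% / 8.4% | 24-38% | 58-65% | 88-97% | 86% |
| 5% / 2% | 38-44% | 3-6% | 44-58% | 42% |
| 1.3% / 0.5% | about 2% | not tabulated | not tabulated | not tabulated |

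The first column counts trials that would be a success under the either rule and a failure under the both rule.

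**The case against.** Much can be said for the plan. The hypothesis puts SSI and dehiscence in front, so haemostasis and satisfaction are visibly lesser aims (objectives 2 and 3). Day 30 is hinted at: the superficial SSI definition in 2.4 uses 30 days, and 3.4 defines loss to follow-up at day 30. The 8-10% needs both literature maxima at once, in a trial limited to elective first-time surgery without uncontrolled diabetes or hypertension, and it needs uncorrected chi-square. With Fisher throughout, the middle case falls below 5%. The indentation of Table 3 is lost, so the reach of its heading is not certain, and five rows become four if SSI is counted once.

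These points limit the size of the problem. None supplies a main outcome, a main visit or a success rule. If the Table 3 heading covered SSI alone, the remaining rows would have no status and dehiscence, half of the hypothesis, would be unranked.

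Three stronger readings should be resisted:
- A reader might infer that any Table 3 row at any visit counts as success, which would put the false-positive risk far above 10%. Testing more rows or visits would add error, but the documents do not state that any row or visit suffices.
- A reader might infer that the error is inflated whichever rule is meant. It is not if both outcomes are required or a composite is tested once.
- A reader might infer that a split result is the likely outcome, or that every rule leaves it unresolved. In all settings examined it is a minority result, and each rule settles it once chosen. The gap is that none is chosen.

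**Conclusion.** The point stands as a gap in the definition of success. Sections 1.3, 1.4, 1.5, 3.7 to 3.10 and Table 3 do not choose between rules that differ materially. Inflation above 5% arises only under the either rule, and its size depends on the event rates and the test. In the direction of benefit, the top-rate figure is 4-5% against 2.5%. The open choice also matters for power: at the top rates with a threefold reduction, requiring both outcomes gives well under the planned 90%, while a composite gives roughly that level.

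The figures rest on 188 per arm, day 30 only, literature rates taken as day-30 rates, and assumed overlap. The gap itself rests on the text alone and does not depend on them.

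**What to change.** Before any comparison by group:

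1. In 3.9, 3.10 and Table 3, name one primary outcome at day 30, tested at two-sided 5% and reported as a risk difference with 95% CI. Recommended: the patient-level composite of any SSI (superficial or deep) or sternal dehiscence by day 30, counted cumulatively, with its components shown.
2. State in 3.7 that P1 and P2 refer to that outcome. Whether 0.15 is a justified rate is a separate question.
3. Put the separate SSI types, dehiscence alone, earlier visits, haemostasis and satisfaction under a secondary heading in Table 3, with CIs and no confirmatory claim.
4. Make 3.10 agree with Tables 1 and 3 on whether dehiscence is part of SSI.
5. State in 3.9 when Fisher's test replaces chi-square.

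If the sponsor instead means that both SSI and dehiscence must improve, the plan should say so as a co-primary rule. No adjustment is then needed, but 3.7 must restate power for two outcomes (about 58-65% at the top rates with a threefold reduction).

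The cost is text only; no new data are needed. A composite weighs a superficial infection the same as a dehiscence, which is why its components must be shown. Haemostasis or satisfaction alone could no longer be presented as primary success.

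### Surgeon satisfaction is an ordered four-level scale, but the documents disagree on its data type, and the test implied by Table 1 ignores the order

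*Combined protocol and SAP*

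**What the plan says.** Section 3.10 gives each satisfaction question "four different response which are satisfied, fairly satisfied, fairly dissatisfied, dissatisfied". Table 1 (Section 3.11) lists the variable as categorical, coded "1 = Satisfied 2 = fairly satisfied 3 = fairly dissatisfied 4 = dissatisfied".

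Section 3.9 assigns methods by data type and does not mention satisfaction by name:

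- Summary of categorical data: "Categorical data analysis will be presented by percentage and frequencies table".
- Test for categorical data: "The proportion comparison tests are applied for comparing categorical independence variable between Sternum Guard™ and bone wax group, such as Chi-square test", with Fisher's exact test as the alternative.
- Test for numerical data: "Mean comparison tests are utilized for comparing numerical independence variable", the examples being "Independent T-Test and Mann-Whitney test for the non-parametric test".

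Table 3 (Section 3.14) attaches a double asterisk to "Satisfaction Rates", and its footnote defines that mark as mean and SD. The four response levels follow as separate rows under N and % columns. In the same table, infection and dehiscence carry the single asterisk for n (%), and haemostasis in grams carries the double one.

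Satisfaction is specific objective 3 in Section 1.5 and a dependent variable in Section 3.8. In Table 3 it stands beneath the Primary Outcomes heading.

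**The concern.** There are two linked problems.

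The first is a conflict over data type. Table 1, the frequency presentation in 3.9 and Table 3's own row layout treat satisfaction as categories. Table 3's marker treats it as a number. Following Table 1 leads to chi-square or Fisher; following the marker leads to a t-test or Mann-Whitney. If this is not settled beforehand, the analyst can choose between two families of test after seeing the data.

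The second is that neither route is well matched to the scale. A Pearson chi-square on a 2 × 4 table spends 3 degrees of freedom and gives the same answer however the four levels are arranged. If one product moves responses steadily towards satisfied, that information is not used. A mean of codes 1 to 4 does use the order, but it treats the step from satisfied to fairly satisfied as equal to the step from fairly dissatisfied to dissatisfied.

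What is at stake is the sensitivity and pre-specification of the analysis for objective 3. The infection result and the sample size are not affected.

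**Working it through.** **1. The plan's own figure.** Section 3.7 uses P1 = 0.15, P2 = 0.05, two-sided alpha 5% and power 90%. The mean proportion is 0.10, so

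n = {1.96 × √(2 × 0.10 × 0.90) + 1.2816 × √(0.15 × 0.85 + 0.05 × 0.95)}² / 0.10² = (0.8316 + 0.5361)² / 0.01 ≈ 187.1.

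This rounds up to 188 per arm, or 376 in total, as stated. Adding 10% gives 376 × 1.10 = 413.6, or 414. The figure rests on a binary outcome and says nothing about power for satisfaction.

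**2. Inputs for satisfaction.** The documents give no response distribution, expected effect or number of surgeons. Assumed here:

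- 188 forms per arm with 1:1 allocation. Table 6 lists 207 devices, half of 414. Forms are completed after surgery, before day-30 loss, so the real number could be nearer 207.
- Independent forms and two-sided alpha 0.05.
- Four illustrative control distributions.
- A common odds ratio (OR) applied to each cumulative split.

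Example: control 50/30/15/5% has cumulative odds 1, 4 and 19. Multiplying by 1.75 gives 1.75, 7 and 33.25, hence cumulative proportions 0.636, 0.875 and 0.971, and levels 63.6/23.9/9.6/2.9%.

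**3. Simulated power (%), 20,000 runs per scenario.**

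| Control split (%) | OR | Chi-square, 3 df | Mann-Whitney | t-test on codes | Mann-Whitney minus chi-square |
|---|---|---|---|---|---|
| 50/30/15/5 | 1.5 | 36.7 | 52.8 | 49.8 | 16.1 |
| | 1.75 | 63.5 | 79.2 | 76.0 | 15.7 |
| | 2.0 | 82.9 | 92.7 | 90.8 | 9.8 |
| 25/25/25/25 | 1.5 | 42.8 | 59.4 | 59.4 | 16.6 |
| | 1.75 | 71.1 | 85.3 | 85.1 | 14.2 |
| | 2.0 | 89.0 | 96.1 | 96.1 | 7.1 |
| 70/20/7/3 | 1.5 | 26.6 | 40.8 | 37.0 | 14.2 |
| | 1.75 | 47.5 | 65.0 | 59.6 | 17.5 |
| | 2.0 | 65.0 | 81.2 | 75.8 | 16.2 |
| 30/40/20/10 | 1.5 | 40.3 | 57.3 | 55.7 | 17.0 |
| | 1.75 | 68.8 | 83.7 | 82.0 | 14.9 |
| | 2.0 | 87.3 | 95.3 | 94.4 | 8.0 |

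With no difference (OR 1), all three tests reject in 4.7 to 5.1% of runs, so the gap is not caused by inflated type I error. The t-test on codes lies 0 to about 5 points below Mann-Whitney.

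**4. Analytic check.** If the whole effect lies in the ordered trend, 80% power on 1 df needs a non-centrality of 7.85. On 3 df it needs 10.90, and 10.90 / 7.85 = 1.39, so about 39% more patients. An effect with 80% power on 1 df has 64% on 3 df. At 90% power the ratio is 14.17 / 10.51 = 1.35.

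**5. A pattern that favours chi-square.** Take 25/25/25/25% against 32/18/18/32%. The mean code is 2.5 in both arms (0.32 + 0.36 + 0.54 + 1.28 = 2.5). Power is 63% for chi-square and 5% for Mann-Whitney and for the t-test.

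**The case against.** The strongest case against the point is that no inefficient test is actually fixed. Section 3.9 never names satisfaction, introduces its tests as examples, and already mentions Mann-Whitney. If Table 3's marker is followed, a rank test is available. This stands: the chi-square route is inferred from the type given in Table 1, and what the documents show is an ambiguity.

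Three stronger readings are tempting and not supported:

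- A reader might infer that both routes throw away the ordering. They do not. A mean of codes 1 to 4 uses it, and the small gap between the t-test and Mann-Whitney shows how little is lost in these scenarios.
- A reader might infer a fixed gain of about 15 points. The documents contain nothing from which to derive one. The gain varies with the assumed distribution and odds ratio, and it becomes a loss for polarised responses.
- A reader might infer that a significant chi-square would leave the preferred product unknown. Table 3 lists every level for both arms under N and %, so direction can be read from the percentages. The Sternum Guard form also asks directly whether the experience was worse, similar or better than with bone wax.

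It is also fair to say that chi-square remains a valid test of any difference, and that the sample size does not depend on satisfaction. These points limit the weight of the concern. They do not resolve the conflict between Table 1 and Table 3, and they do not supply an ordered test for the categorical route.

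**Conclusion.** The point holds in a limited form. Table 3's mean and SD marker conflicts with the categorical type in Table 1, with the frequency presentation in 3.9 and with Table 3's own layout. Read through Table 1, the implied test ignores order.

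Under assumed proportional-odds shifts with OR 1.5 to 2.0 and 188 independent forms per arm, that test has roughly 7 to 18 points less power than a rank test. This size rests on three assumptions: the response distributions, a shift in one direction along the scale, and independence. A one-directional shift is the natural meaning of greater satisfaction, but it is not guaranteed. Each surgeon presumably rates several operations, and the absolute powers would be too high if surgeons differ in which product they prefer.

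This is a minor matter of consistency and efficiency, worth correcting because satisfaction is a stated objective and the correction is cheap.

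**What to change.** - **Table 3:** change the satisfaction marker from mean and SD to n (%) per level, and state that the rows show the overall satisfaction item. The questionnaire has five items, and Table 3 does not say which is reported.
- **Section 3.9:** name satisfaction explicitly and prespecify an ordered comparison of the overall item. A proportional-odds model with surgeon-clustered standard errors is preferable, reporting a common odds ratio with 95% CI. State its direction, because code 1 is the most favourable answer. Mann-Whitney is the simple alternative, but it gives neither the odds ratio nor an allowance for surgeon.
- **Questionnaire:** make the operating surgeon identifiable on each form. The present fields are time and date, investigator, group and patient's initial, and none is labelled surgeon.

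The cost is one marker, a sentence or two in 3.9 and possibly one field on the form, with no extra patients and no change to 376. The downsides are small: less sensitivity to polarised responses, which the n (%) table would still show, and reliance on the proportional-odds assumption, which should be checked. The number of surgeons is not stated. If it is small, clustered standard errors become unreliable, and surgeon could enter the model as a stratum or random effect instead.
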